9.8. Warnings and Precautions

Special warnings or precautions for the study drug, derived from safety information collected by the sponsor or its designee, are presented in the [IB](#). Additional safety information collected between IB updates will be communicated in the form of Investigator Notifications. Any important new safety information should be discussed with the participant during the study as necessary. If new significant risks are identified, they will be added to the ICF.

9.9. Product Complaints

The sponsor collects product complaints on study drugs and drug delivery systems used in clinical studies in order to ensure the safety of study participants, monitor quality, and facilitate process and product improvements.

All product complaints associated with material packaged, labeled, and released by the sponsor or its designee will be reported to the sponsor. All product complaints associated with other study material will be reported directly to the respective manufacturer.

The investigator or his/her designee is responsible for reporting a complete description of the product complaint via email or other written communication to the sponsor contact or respective manufacturer as noted in the packaging information. Any AE associated with a product complaint should be recorded as described in Section [9.3](#).

If the investigator is asked to return the product for investigation, he/she will return a copy of the product complaint communication with the product.

9.10. Treatment of Overdose

There has been no clinical experience with overdose of ruxolitinib cream. Treatment of overdose should consist of general supportive measures.

10. STATISTICS

10.1. Sample Size Determination

Approximately 75 participants will be randomized 2:1 to ruxolitinib cream 1.5% BID or vehicle BID. The sample size calculation is based on the Fisher exact test for the primary efficacy endpoint. Based on the results from the 2 pivotal studies, INCB 18424-303 and -304, the response rate of EASI75 at Week 4 on head and neck is assumed to be 55% for the active arm of 1.5% BID versus 15% for placebo. Using a 2-sided alpha of 0.05, the sample size will have a > 90% power to detect a difference between the active treatment group versus vehicle. In addition, to provide adequate power for efficacy variables, the sample size is determined to provide a large database for safety evaluation.

10.2. Populations for Analysis

The populations for analysis are provided in [Table 8](#).

Table 8: Populations for Analysis

Population	Description
FAS	The FAS includes all participants enrolled in the study who will have at least 1 application of study drug. The FAS will be used for the summary of demographics, baseline characteristics, participants disposition, and analyses of all efficacy and safety data.
OL-evaluable	The OL-evaluable population includes all participants who applied at least 1 dose of ruxolitinib cream during the OL period. All analyses for the OL period will be conducted with the OL-evaluable population.

10.3. Level of Significance

A hypothesis test will be conducted for the primary analysis at the 2-sided alpha = 0.05 level. In addition, 95% CI will be reported, if applicable.

10.4. Statistical Analyses

10.4.1. Primary Analysis

The primary endpoint of this study is the proportion of participants who achieve an EASI75 of the head and neck region at Week 4. The primary analysis will be based on the FAS population. The primary alternative hypothesis (superiority of ruxolitinib 1.5% BID compared with vehicle) will be tested using a CMH test stratified by the stratification factor (screening face and/or neck IGA score). Odds ratio in response rates (ruxolitinib cream vs vehicle) at Week 4 will also be computed, and p-values will be provided. The difference in proportion of participants who achieve an EASI75 score of the head and neck region (ruxolitinib cream vs vehicle) at Week 4 will also be computed.

All nonresponders in the DB treatment period, as well as all participants who discontinue study treatment at any time before the timepoint of interest, or withdraw from the study for any reason, will be defined as nonresponders for the nonresponder imputation analysis.

10.4.2. Secondary [REDACTED] Analyses

All secondary [REDACTED] efficacy variables will be summarized using descriptive statistics. For categorical measurements, summary statistics will include sample size, frequency, and percentages. For continuous measurements, summary statistics will include sample size, mean, median, standard deviation, standard error of the mean, minimum, and maximum. Continuous efficacy endpoints, including the actual measurement, change from baseline, and percentage change from baseline may also be analyzed by the mixed-effect model with repeat measurement.

10.4.3. Safety Analyses

A TEAE is any AE either reported for the first time or worsening of a pre-existing event after first dose of study drug. Analysis of AEs will be limited to TEAEs, but data listings will include all AEs regardless of their timing to study drug administration. Adverse events will be tabulated by the MedDRA preferred term and system organ class. Severity of AEs will be based on the NCI CTCAE v5.0 using Grades 1 through 5.

The subset of AEs considered by the investigator to have a relationship to study drug will be considered to be treatment-related AEs. If the investigator does not specify the relationship of the AE to study drug, then the AE will be considered treatment-related. The incidence of AEs and treatment-related AEs will be tabulated.

Descriptive statistics and mean change from baseline will be determined for vital signs (blood pressure, pulse, respiratory rate, and body temperature) at each assessment time.

10.5. Interim Analysis

No formal interim analysis is planned in this study.

11. SUPPORTING DOCUMENTATION AND OPERATIONAL CONSIDERATIONS

11.1. Investigator Responsibilities

- The Protocol, Protocol amendments, ICF, IB, and other relevant documents (eg, advertisements) must be submitted to an IRB/IEC by the investigator and reviewed and approved by the IRB/IEC before the study is initiated.
- The investigator is responsible for ensuring that the safety reports provided by the sponsor are reviewed and processed in accordance with regulatory requirements, the policies and procedures established by the IRB/IEC, and institutional requirements.
- Any amendments to the Protocol will require approval from both health authorities and IRB/IEC before implementation of changes made to the study design, except for changes necessary to eliminate an immediate hazard to study participants.
- The investigator will be responsible for the following:
 - Providing written summaries of the status of the study to the IRB/IEC annually or more frequently in accordance with the requirements, policies, and procedures established by the IRB/IEC.
 - Notifying the IRB/IEC of SAEs or other significant safety findings as required by IRB/IEC procedures.
 - Providing oversight of the conduct of the study at the site and adherence to GCP, IRB/IEC requirements, institutional requirements, and applicable laws and country-specific regulations.
- Adhering to the Protocol as described in this document and agreeing that changes to the Protocol procedures, with the exception of medical emergencies, must be discussed and approved, first, by the sponsor or its designee and, second, by the IRB/IEC. Each investigator is responsible for enrolling participants who have met the specified eligibility criteria.
- Retaining records in accordance with all local, national, and regulatory laws but for a minimum period of at least 2 years after the last marketing application approval in an ICH region and until there are no pending or contemplated marketing applications in an ICH region, or if not approved, 2 years after the termination of the test article for investigation to ensure the availability of study documentation should it become necessary for the sponsor or a regulatory authority to review.
 - The investigator must not destroy any records associated with the study during the retention period without receiving approval from the sponsor. The investigator must notify the sponsor or its designee in the event of accidental loss or destruction of any study records. If the investigator leaves the institution where the study was conducted, the sponsor or its designee must be contacted to arrange alternative record storage options.

- All eCRF data entered by the site (including audit trail), as well as computer hardware and software (for accessing the data), will be maintained or made available at the site in compliance with applicable record retention regulations. The sponsor will retain the original eCRF data and audit trail.

11.2. Data Management

Data management will be performed in a validated EDC system. The investigator will be provided with access to an EDC system so that an eCRF can be completed for each participant.

The site will be provided with eCRF completion guidelines for instructions on data entry in the eCRF. The study monitor will reference the Monitoring Plan in order to ensure that each issue identified is appropriately documented, reported, and resolved in a timely manner in accordance with the plan's requirements. Other data outside the EDC system required in the study conduct of the Protocol, such as documents or results transmitted to the sponsor via a central laboratory or specialized technical vendors and as designated by the sponsor, will have their own data flow management plans, study charters, or biomarker plans, as applicable.

The sponsor (or designee) will be responsible for the following:

- Managing the integrity of the data and the quality of the conduct of the study, such as ensuring that study monitors perform ongoing source data verification to confirm that data entered into the eCRF by authorized site personnel are accurate, complete, and verifiable from source documents; that the safety and rights of participants are being protected; and that the study is being conducted in accordance with the currently approved Protocol and any other study agreements, ICH GCP, and all applicable regulatory requirements.
- Managing and reconciling the data generated and/or collected, including documents and results such as laboratory or imaging data analyzed centrally by a designated vendor of the sponsor.

The investigator will be responsible for the following:

- Recording, or ensuring the recording of, all relevant data relating to the study in the eCRF.
- Delivering, or ensuring the delivery of, all other results, documents, data, know-how, or formulas relating to the study to the sponsor or designee electronically and/or centrally (eg, laboratory data, imaging data, biomarker data, photographs, diary data) or as otherwise specified in the Protocol.
- Maintaining adequate and accurate source documents and trial records that include all pertinent observations on each of the site's trial participants. Source data should be attributable, legible, contemporaneous, original, accurate, and complete. Changes to source data should be traceable, should not obscure the original entry, and should be explained if necessary (eg, via an audit trail). Source data are, in general, all information in original records and certified copies of original records of clinical findings, observations, or other activities in a clinical trial necessary for the reconstruction and evaluation of the trial. Source data are contained in source documents (original records or certified copies).

- Verifying that data entries are accurate and correct by physically or electronically signing the eCRF.
- Maintaining accurate documentation (source data) that supports the information entered in the eCRF, sent to a central vendor designated by the sponsor, or as described in other study and data flow manuals.
 - Source documents provide evidence for the existence of the participant and substantiate the integrity of the data collected. Source documents are filed and available at the investigator's site. Examples of source documents are original documents, data, and records (eg, hospital records; electronic hospital records; clinical and office charts; laboratory notes; memoranda; participants' diaries or evaluation checklists, pharmacy dispensing records, recorded data from automated instruments; copies or transcriptions certified after verification as being accurate copies; microfiches; photographic negatives; microfilm or magnetic media; x-rays; participants' files; and e-records/records kept at the pharmacy; at the laboratories, and at medico-technical departments involved in the clinical trial).
 - Data entered in the eCRF that are transcribed from source documents must be consistent with the source documents or the discrepancies must be explained. The investigator may need to request previous medical records or transfer records, depending on the study. Current applicable medical records must be available.
- Sending participants' data, either as unique samples, or copies, or photographs, to be evaluated centrally or analyzed centrally, or both, by a qualified vendor designated by the sponsor.
 - As required by privacy and data protection regulations and Incyte's privacy policies, if any photographs of participants are to be taken, the photographs must be limited to the area of the face or the body that is strictly necessary and the photographs should be masked (ie, identifying features such as eyes, mouth, scars, tattoos, or unique markings or features should be either obscured with a black bar or digitally pixelated so as to not permit the reidentification of the participants and preserve their confidentiality) by a specially designated photography vendor prior to sending the photographs to Incyte or any other third-party vendors for analysis or further processing.
- Permitting study-related monitoring, sponsor audits, IRB/IEC review, and regulatory inspections by providing direct access to source data and other relevant clinical study documents.
 - Monitoring: Qualified representatives of the sponsor or its designee, study monitors, will monitor the study according to a predetermined plan. The investigator must allow the study monitors to review any study materials and participant records at each monitoring visit.

- Auditing: Qualified representatives of the sponsor or its designee may audit the clinical study site and study data to evaluate compliance with the Protocol, applicable local clinical study regulations, and overall study conduct. The investigator must allow the auditors to review original source records and study documentation for all participants.
- Regulatory inspection: Regulatory authorities may conduct an inspection of the study and the site at any time during the development of an investigational product. The investigator and staff are expected to cooperate with the inspectors and allow access to all source documents supporting the eCRFs and other study-related documents. The investigator must immediately notify the sponsor when contacted by any regulatory authority for the purposes of conducting an inspection.

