2.2.1. Scientific Rationale for Study Design

Two Phase 3 pivotal studies (INCB 18424-303 and INCB 18424-304) demonstrated that ruxolitinib 1.5% cream BID was statistically significantly superior to vehicle after 8 weeks of treatment for the primary endpoint, IGA-TS (a score of 0 or 1 with \geq 2 grade improvement from baseline), and key secondary endpoints, including a 75% improvement in the EASI and at least a 4-point improvement in the Itch NRS ([Papp et al 2020](#)). The 1.5% strength was also superior in

efficacy to the 0.75% strength with nondifferentiating safety profiles of both regimens. The purpose of this study is to further investigate and confirm the efficacy and safety of ruxolitinib cream (1.5%) when applied to affected areas on the face and neck.

This study will be a fully DCT. The benefits of a DCT include enhancing the participant's experience, minimizing day-to day disruption, eliminating travel burden, potentially increasing participant diversity, and improving participant retention. All visits will be conducted remotely via telemedicine (telephone and/or video) or in-home visits by a trained mobile healthcare provider. Efficacy assessments will be performed by an investigator/rater (dermatologist; central reader) using high-quality digital photographs. A validation study demonstrated excellent agreement between assessment of AD severity using EASI, SCORAD, IGA, and BSA during in-home visits and via digital photographs ([Hughes et al 2019](#)).

This study will enroll both male and female participants \geq 12 years of age with both an overall and a face and/or neck IGA score of 2 or 3 and AD affecting at least 0.5% of the total BSA on the face or neck. Participants in the Phase 3 studies had AD involvement of 3% to 20% BSA (excluding the scalp) and an IGA score of 2 to 3 at baseline. Although approximately 39% of participants with AD in the Phase 3 studies reported prior facial involvement, the efficacy assessments in these studies (eg, IGA-TS and EASI) were based on the all (total) AD-affected areas. The study population for this trial will be similar to the Phase 3 study population with the exception that in this study, all participants must have AD lesions on the face and/or neck region involving at least 0.5% of their total BSA in that area.

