8.2. Efficacy Assessments

The investigator or designee will independently assess the ClinROs (EASI, [REDACTED] and %BSA involvement) via the digital photographs. Rater performing the assessment will be distinct from the investigator conducting the televisit. If possible, the same rater should perform the assessment for the same participant at every visit. At the baseline visit, clinical assessments (eg, IGA, BSA) need to be completed during the visit prior to first study drug application.

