8.2.1. Full-Body Photography

For the ClinRO assessments (EASI, [REDACTED] and BSA), full body photographs will be captured by the mobile healthcare provider at the visits designated in [Table 3](#). The photograph set will undergo a quality-control process to ensure photographs are of sufficient quality for ClinRO assessments. The rater (a dermatologist) will rate the participant's AD severity using the specified ClinRO assessments described in Sections [8.2.2](#), [8.2.3](#), and [8.2.4](#). The mobile healthcare provider will be trained to take a standard set of full-body photographs. A reference guide will be provided to the mobile nurse for photo capture during the remote visit. An investigator will provide oversight during the photography capture process to determine in real-time if the photographs obtained are of sufficient quality. Photographs not meeting the assessment standard will be retaken during the same session.

The investigator or designee will document in the eCRF the specific affected areas of the face (forehead, cheeks, chin, nose, eyelids, periocular, and mouth) and other body areas based on the photographs.

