5. Section 1, Protocol Summary; Section 5.4, Screen Failures; Section 6.2, Preparation, Handling, and Accountability; Section 7.3, Lost to Follow-Up; Section 8.1.2, Screening Procedures; Section 8.1.4, Distribution of Reminder Notification and eDiary

Description of change: Minor revisions and clarifications made to text.

Rationale for change: To align with DCT model.

7. Section 1, Protocol Summary (Table 3: Schedule of Activities)

Description of change: Added that study drug will also be collected during Week 4 at the end of the DB VC period.

Rationale for change: The study drug collection during Week 4 was inadvertently excluded from the table.

8. Section 2.2, Study Rationale

Description of change: Updated to include the details of the approval of ruxolitinib 1.5% cream.

Rationale for change: To provide most up to date information.

9. Section 2.2.1, Scientific Rationale for Study Design; Section 8.2, Efficacy Assessments

Description of change: Revised to include a rater in addition to an investigator for efficacy assessments.

Rationale for change: To clarify that clinical assessments are assessed independently by rater(s) and not the investigator(s).

10. Section 5.2, Exclusion Criteria (Exclusion Criterion 4b)

Description of change: Updated washout to 4 weeks.

Rationale for change: To be consistent with other ruxolitinib cream study protocol(s) considering the short half-life of these immunomodulating agents.

11. Section 5.2, Exclusion Criteria (Exclusion Criterion 7c)

Description of change: Revised criteria to clarify the exception for the ULN of total bilirubin applies to participants with Gilbert's Syndrome.

Rationale for change: To clarify the relationship between the total versus direct bilirubin criteria.

12. Section 5.2, Exclusion Criteria (Exclusion Criterion 8); Section 8.5.3, Laboratory Assessments (Table 7: Required Laboratory Analytes); Section 8.5.3.2, Serology

Description of change: Revised HBV and HCV criteria for participants who are positive for HCVAb, which requires additional laboratory assessments of HCV RNA. Updated language to be consistent with the laboratory testing procedures and clarified requirements for test results.

Rationale for change: Due to DCT model, all required HBV and HCV tests are to be performed at the same time (ie, no reflective tests).

13. Section 5.3, Lifestyle Consideration

Description of change: Updated to address participant's living environment and schedule.

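### Does the photograph-masking rule in Protocol 11.2 hide facial skin that the head and neck EASI has to score?

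*Protocol*

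**What the plan says.** **Masking.** Protocol 11.2 lists, among the investigator's duties, sending participant data such as "photographs, to be evaluated centrally or analyzed centrally, or both, by a qualified vendor designated by the sponsor". A sub-item under that duty says that if photographs are taken, "identifying features such as eyes, mouth, scars, tattoos, or unique markings or features should be either obscured with a black bar or digitally pixelated". A designated photography vendor does this "prior to sending the photographs to Incyte or any other third-party vendors for analysis or further processing".

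**Scoring.** Protocol 2.2.1 states: "Efficacy assessments will be performed by an investigator/rater (dermatologist; central reader) using high-quality digital photographs". Protocol 8.2 opens with "The investigator or designee will independently assess the ClinROs" and adds that the rater is a different person from the investigator on the televisit. Protocol 8.2.1 has a dermatologist do the rating, after a quality check that the set is fit for that purpose, and poor images are retaken in the same session. It also has the investigator or designee make an eCRF entry of "specific affected areas of the face (forehead, cheeks, chin, nose, eyelids, periocular, and mouth) and other body areas based on the photographs". SAP 7.3 says only that digital photographs are the source of the clinician-reported outcomes.

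**Region.** Protocol 8.2.2 and SAP 7.3.1.1 define the head and neck as one EASI region, scored 0 to 7.2, with each sign graded by its average severity over the region. Neither excludes any facial skin.

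**The concern.** A black bar over the eyes and mouth hides much of the eyelid, periocular and perioral skin. If the rater saw only such images, disease there could be neither recorded nor graded. The regional average behind the primary endpoint would then come from a smaller area than the definition implies. EASI75 is a percentage change, so it would also matter whether the same skin was hidden at baseline and at Week 4.

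Several phrases suggest that the rater might be covered by the rule. Section 2.2.1 calls the scorer a central reader. Section 11.2 speaks of central evaluation by a vendor directly above the masking text. The rationale for item 9 of Amendment 2 says that rating is meant to be done by raters rather than investigators. No readable sentence in either document says whether the rating images are masked.

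**Working it through.** The question is mainly one of text, so the passages are set side by side first.

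1. **What triggers masking.** The trigger is sending images to the sponsor or to another third-party vendor ("prior to sending the photographs to Incyte or any other third-party vendors for analysis or further processing"). The rule does not govern viewing at the site or by the investigator's own designee.

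2. **Who looks at the images.** Protocol 4.1 says the mobile healthcare provider takes the photographs so that the investigator can make the clinician-reported assessments. SAP 3 likewise has the investigator use the photographs for the Week 4 assessments. Protocol 8.2 gives the task to the investigator or designee. Section 2.2.1 joins investigator and rater in one term and adds central reader in brackets. A central reader may be a vendor, but the term does not say so.

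3. **Two cases.**
   - *The rater works on the investigator's side.* Section 11.2 is not triggered for scoring. The rater uses unmasked images, masked copies go to the sponsor and vendors, and both sections are met.
   - *The rater is a third-party vendor.* Section 11.2, read literally, would reach the rating images and conflict with 8.2.1. The conflict would be between general advice and a study-specific requirement. Section 11.2 says should, and is conditional on photographs being taken at all, although this trial schedules them at every visit from screening on. That reads as standard sponsor wording. Section 8.2.1 was written for this trial, names the eyelids, periocular area and mouth, and requires images that can be scored. A team following the protocol would give the rater such images.

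4. **What is not visible.** The protocol's contents list shows section 8.4.1, on the location of affected areas, but its text is absent from the public copy. Section 11.2 also refers to separate data flow plans and charters for data held outside the EDC system, which are not supplied. Silence can be claimed only for the readable text.

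5. **Numbers, for context.** Protocol 10.1 and SAP 3.3 assume 55% against 15% response, 75 participants at 2:1 (50 and 25), two-sided alpha 0.05, Fisher's exact test and power above 90%. Exact enumeration gives 93.8%, so the stated figure reproduces.

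   To see what would be at stake, assume that hidden skin flips the EASI75 classification at the same rate *e* in both arms. The observed rate is then p' = p(1 − e) + (1 − p)e.

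| e (assumed) | Active | Vehicle | Fisher power |
|---|---|---|---|
| 0 | 55% | 15% | 93.8% |
| 5% | 54.5% | 18.5% | 86% |
| 10% | 54% | 22% | 75% |
| 15% | 53.5% | 25.5% | 62% |
| 20% | 53% | 29% | 48% |

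   None of these values of *e* comes from the documents. The table describes a masked rating process that has not been shown to exist. Even in that process, when the true rates are equal the observed rates stay equal, so an equal flip rate does not inflate the type I error.

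**The case for a change.** The best case for acting is that Protocol 11.2 is current text, that 11.1 obliges the investigator to follow the protocol as written, and that no exception for rating images is stated. In a trial of facial disease rated from photographs, which skin the rater can see is close to being part of the endpoint definition. One sentence would settle it at almost no cost.

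Part of this stands. The readable text is silent, and a cross-reference would be tidy. The rest does not show a fault. Masked rating is not shown and no bias toward either arm is argued. The defined region is the whole head and neck, and nothing narrows it. The evidence that the rater is a vendor is thin. The 11.2 item on central evaluation is a generic list that names neither EASI nor the rater, and the description of Amendment 2 item 9 speaks of a rater in addition to an investigator. The 11.2 item on delivering data, photographs included, also allows for arrangements specified elsewhere in the protocol.

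**Conclusion.** No change follows. This is a missing operational detail that the study team can fill sensibly from the text it already has: rate from images fit for scoring, and mask the copies that are transferred. Followed that way, the plan gives a sound head and neck EASI75 and the analysis is unaffected.

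No size can be attached to the point. Mask dimensions, image routing and the frequency of eyelid or perioral disease are not given, and the power losses tabulated above rest wholly on assumed rates.

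The conclusion assumes that the rater sees unmasked images, which is the natural reading of 8.2.1, and that neither the missing text of 8.4.1 nor an imaging charter says otherwise. Evidence that raters were in fact given masked images would reopen the question.
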